## SYNOPSIS OF PROTOCOL

Study Title	An Open-Label, Phase II Study of Anlotinib Treatment in Patients With Recurrent or Metastatic Nasopharyngeal Carcinoma after failure of no less than second-line chemotherapy or targeted therapy
Study Objective	This is a single-arm study designed to evaluate the efficacy and safety of anlotinib hydrochloride in the treatment of patients with recurrent or metastatic nasopharyngeal carcinoma after failure of second-line or above chemotherapy or targeted therapy.
Study Design	Single-arm trial
Study Drug	Anlotinib hydrochloride
Study Population	Patients with recurrent or metastatic nasopharyngeal carcinoma after failure of second-line or above chemotherapy or targeted therapy
Sample Size	39
Treatment Regimen	Anlotinib hydrochloride will be administered orally at a dose of 12 mg once a day before breakfast, for 2 consecutive weeks, and discontinued for 1 week, i.e., three weeks (21 days) as a course of treatment. Treatment should continue until disease progression or occurrence of intolerable toxicity.
Study Period	Start date of enrollment: March 2019; End date of enrollment: March 2021; Expected date of last follow-up: March 2026.
Efficacy Endpoints	Disease control rate (DCR), overall response rate (ORR), progression free survival (PFS), overall survival (OS), complete remission (CR), partial remission (PR) and

	duration of response (DOR)
Safety Endpoints	Symptoms and signs, observed toxic reactions of chemotherapy, laboratory parameters, adverse events (AEs) and serious adverse events (SAEs)
Efficacy Evaluation	According to RECIST 1.1
Safety Evaluation	According to NCI-CTC AE 4.0
Quality of Life Evaluation	FACT-H&N (V4) Quality of Life questionnaire
Statistical Methods	In this single-arm study, the data will be analyzed mainly using descriptive statistics, with log-rank test for efficacy endpoint analysis and descriptive method and percentage for safety analysis.

## **1. STUDY BACKGROUND**

### **1.1 Epidemiology of Nasopharyngeal Carcinoma and Current Treatment Modalities**

Nasopharyngeal carcinoma (NPC) is a special type of malignant cancer of the head and neck with an extremely imbalanced geographical distribution. It is also referred to as "Canton tumor" due to a high incidence in Southern China. In 2012, there were 86,700 new cases of NPC reported globally, with the highest incidence in Southeast Asia. The non-keratinizing pathological subtype accounts for more than 95% of NPC cases, which is highly sensitive to chemoradiotherapy. For patients with early-stage or locally advanced NPC, the standard treatment regimen is concurrent chemoradiotherapy, with 5-year survival rates of over 87%–96% for patients with early-stage NPC after treatment. However, clinical studies showed that after the first course of treatment, 10%–36% of NPC patients still suffer from locally recurrent NPC, of which 65%–85% occur during the first 3 years after treatment. In addition, about 15% of NPC patients have distant metastases at the time of diagnosis. Patients with recurrent and/or metastatic NPC have a poor prognosis, with a median OS of only 20 months.

### **1.2 Chemotherapy Regimens for Advanced Recurrent or Metastatic Nasopharyngeal Carcinoma**

At present, the first-line chemotherapy for recurrent or metastatic NPC has been gradually standardized, and platinum-based doublet chemotherapy regimens are widely used in clinical practice. The drugs used in combination chemotherapy include 5-fluorouracil (5-Fu), paclitaxel, docetaxel, gemcitabine and capecitabine. The most widely used combination chemotherapy regimen for patients with recurrent metastatic NPC has been the combination of 5-Fu with cisplatin (PF), but it has poor efficacy,

with an objective response rate of 40%–60% and a median OS of 15–20 months. In addition, this regimen has the disadvantages of severe toxic and side effects such as stomatitis and inconvenient use. In a phase II clinical study by Chen et al., the combination of paclitaxel with cisplatin (TP) as first-line treatment in patients with recurrence and metastasis showed a remission rate of 79%, PFS of 8.6 months and OS of 22.7 months. In another study, the combination of lobaplatin with docetaxel as first-line chemotherapy for recurrent and metastatic NPC showed an overall response rate of 61.5% and a PFS of 10.0 months. In August 2016, Lancet published online the phase III clinical findings of [name] and his team on the combination of gemcitabine + cisplatin (GP) versus PF for the treatment of recurrent or metastatic NPC. The GP regimen showed a better objective response rate (64% vs. 42%), PFS (7.0 months vs. 5.6 months) and OS (29.1 months vs. 20.1 months), 45% risk reduction in disease progression, and 38% risk reduction in death, compared with the PF regimen, with a similar overall incidence of adverse events. Unfortunately, 10% of the subjects treated with GP failed to achieve disease control (90% DCR), more than 30% of the subjects failed to achieve disease remission (64% ORR), and the median progression-free survival was only 7 months.

Although the efficacy of first-line chemotherapy for recurrent or metastatic nasopharyngeal carcinoma has been confirmed, a significant proportion of patients still experience disease progression after receiving first-line chemotherapy. There is no particularly effective treatment option available for patients failing first-line chemotherapy. Although second-line chemotherapy drugs such as gemcitabine and capecitabine have shown certain efficacy, they failed to result in a significant improvement in median survival, which was only 7–11 months. It is difficult for NPC patients with distant metastasis to achieve a durable response. Most patients experience disease progression in a short period time after initial response, and the site of recurrence usually becomes resistant to chemotherapy. Therefore, there is an urgent need to develop novel therapeutic drugs to provide effective treatment options for patients with recurrent/metastatic NPC after the failure of two or more lines of chemotherapy or targeted therapy.

### 1.3 Study on Target for Anti-angiogenic Therapy in the Treatment of Nasopharyngeal Carcinoma

Tumors depend on angiogenesis for continuous replication and tumor growth. As early as in 1971, Folkman, an American scholar, firstly proposed that tumor growth was closely related to blood vessels and pointed out that tumors could be treated by blocking the growth of blood vessels. Vascular endothelial growth factor (VEGF), one of the most important angiogenic factors, can directly act on vascular endothelial cells to stimulate their mitosis, thus promoting the growth of new blood vessels. The angiogenesis pathway is one of the current focuses of drug research and development, and a number of drugs have been developed, including monoclonal antibodies and small molecule tyrosinase inhibitors (Table 1).

Table 1. Research progress on VEGF-targeted anti-angiogenic drugs

English Drug Name	Chinese Drug Name	Trade Name	Drug Type	Drug Sensitivity Testing	Remarks (Lung Cancer)	Indications (except Lung Cancer)
Bevacizumab	贝伐珠单抗	Avastin/安维汀	Monoclonal antibody	VEGF	First line (America, China)	Metastatic colorectal carcinoma, malignant glioma, metastatic renal cell carcinoma, cervix carcinoma, ovarian cancer
Ramucirumab	雷莫芦单抗	Cyramza	Monoclonal antibody	VEGFR2	Second line (America)	Colorectal carcinoma, gastric cancer
Nintedanib	尼达尼布	Ofev	Small molecule	VEGFR1-3, PDGFR $\alpha/\beta$ , FGFR1-3, etc.	Second line (Europe)	Pulmonary fibrosis
Endostatin	重组人血管内皮抑制素注射液	Endostar	Recombinant human endostatin	Suppressing tumor angiogenesis through inhibiting vascular endothelial cell migration	First/second line (China)	None
Drugs under development						
Anlotinib	安罗替尼		Small molecule	VEGFR1-3, PDGFR $\alpha/\beta$ , FGFR1-3, etc.	Third line (success)	None
Apatinib	阿帕替尼		Small molecule	VEGFR2	Third line (phase III in progress)	Gastric cancer
Sunitinib	舒尼替尼	Sutent	Small molecule	KIT, PDGFR $\beta$ , VEGFR1-3, etc.	Two or more lines (failure)	GIST, renal cell carcinoma, pancreatic neuroendocrine tumor
Sorafenib	索拉菲尼	Nexavar/多吉美	Small molecule	KIT, PDGFR $\beta$ , VEGFR1-3, etc.	Third line (failure)	Hepatocellular carcinoma, renal cell carcinoma, differentiated thyroid carcinoma
Fruquintinib	呋喹替尼		Small molecule	VEGFR1-3, FGFR1, KIT, etc.	First line (phase III in progress)	None

Studies showed that overexpression of vascular endothelial growth factor-a (VEGF-A) associates with poor prognosis in head and neck squamous cell carcinoma (HNSCC). A meta-analysis of 1002 cases of HNSCC from 12 studies investigated the VEGF-A expression and found that the 2-year mortality rate in HNSCC subjects with VEGF-positive staining was twice that in negative subjects. One study confirmed that VEGF plays a crucial role in the induction of angiogenesis and lymph node metastasis in NPC. In another study, Qian et al. found significant increases in serum VEGF levels in 65 subjects with metastatic NPC. The study results showed that 67% of NPC subjects showed VEGF overexpression, and VEGF expression was higher in subjects with EBV-positive tumors and was associated with increased recurrence rate, positive lymph node ratio, and decreased survival. A preliminary study by Druzgal et al. demonstrated that serum cytokines and angiogenic factors can be used as markers for judging the efficacy in subjects with head and neck cancers before and after treatment. At a mean follow-up of 37 months, subjects with decreased VEGF levels after treatment maintained longer disease remission than those with elevated VEGF levels after treatment. In this study, 7% of subjects were NPC patients.

Anti-angiogenic target also gradually becomes a hot topic in NPC clinical study. In a North American multicenter phase II study (RTOG 0615) reported in *Lancet Oncology* in 2012, bevacizumab plus chemoradiotherapy for locally advanced NPC (stage IIB–IVB) showed a 2-year OS of 90.9% and a 2-year PFS of 74.7%. No Grade 3–4 hemorrhage and Grade 5 adverse events occurred in this study, suggesting the efficacy and tolerability of bevacizumab plus chemoradiotherapy for locally advanced NPC, which is expected to improve patients' survival. In a study reported in *Annals of Oncology* in 2013 regarding the combination of sorafenib with PF as a second-line treatment in 54 patients with recurrent or metastatic NPC, the PFS and OS, as two primary study endpoints were 7.2 months and 11.8 months, respectively, and the major adverse reactions included hand and foot syndrome, myelosuppression and gastrointestinal reactions, which the patients could tolerate. This study demonstrated

the feasibility of sorafenib plus PF regimen for the treatment of recurrent or metastatic NPC. In a single-arm exploratory single-agent study of sunitinib in 14 patients with recurrent or metastatic NPC after radiotherapy and multiple lines of chemotherapy, tumor shrinkage occurred in 5 out of the 10 patients who underwent at least one radiological evaluation, also suggesting the efficacy of sunitinib in patients with recurrent or metastatic NPC.

#### **1.4 Mechanism of Action of Anlotinib**

Anlotinib hydrochloride (AL3818) is a novel small molecule multi-target tyrosine kinase inhibitor, belonging to anti-angiogenic agents. Its principal mechanism of action is as follows: 1) Marked inhibitory activity against angiogenesis-related kinases, such as vascular endothelial growth factor receptor (VEGFR) 1/2/3, fibroblast growth factor receptor (FGFR) 1/2/3, and other tumor cell proliferation-related kinases, such as platelet-derived growth factor receptor (PDGFR)  $\alpha/\beta$ , c-Kit and Ret. It can inhibit a broader spectrum of angiogenic kinases (e.g., Met, FGFR1/2/3). 2) Marked inhibitory activity against some kinase targets under studies, such as Aurora-B, c-FMS and DDR1. 3) Marked inhibitory activity against various kinase mutants, such as PDGFR $\alpha$ , cKit, Met and epidermal growth factor receptor (EGFR). The inhibitory activity against the mutants is even stronger than that against the wild type. This drug is developed independently in China and belongs to class 1.1 anti-cancer new drugs.

The maximum tolerated dose identified in the preliminary study was 12 mg qd in the dose-finding study. Through tolerance observation in 21 subjects successively, 12 mg qd for 2 consecutive weeks followed by 1-week discontinuation was generally recognized as the recommended regimen for subsequent studies, and 12 mg qd was the maximum tolerated dose.

#### **1.5 Clinical Efficacy of Anlotinib**

Several clinical studies have demonstrated the clinical efficacy of anlotinib. In a phase I clinical study of anlotinib in the treatment of multiple solid tumors including colon

adenocarcinoma, non-small cell lung cancer (NSCLC), clear cell renal cell carcinoma, medullary thyroid cancer and soft tissue sarcoma, 20 patients were evaluated for the antitumor activity of anlotinib, with PR in 3 cases, SD in 14 cases, and disease progression in 3 cases. The major adverse reactions included hypertension, increased triglycerides, hand and foot skin reaction, and increased lipase. This study showed that anlotinib had a good safety profile and broad-spectrum antitumor activity, providing a basis for further studies.

In a randomized controlled, double-blind, nationwide multicenter phase II clinical study (ALTER302) of anlotinib for the treatment of non-small cell lung cancer, the safety and efficacy of anlotinib as a third-line treatment in patients with advanced refractory NSCLC was evaluated. A total of 117 patients were enrolled in the study and were randomized to the placebo control group and the anlotinib group (12 mg qd). The study results showed a better PFS (4.8 months vs. 1.2 months), overall response rate (ORR, 10.0% vs. 0%) and mean OS (9.3 months vs. 6.3 months) in the anlotinib group than in the placebo group. In terms of safety, the incidence of Grade 3–4 adverse reactions in the anlotinib group was only 21.67%.

ALTER0303 was a multicenter, randomized, double-blind, placebo-controlled, parallel-group phase III clinical trial involving 437 patients with advanced metastatic NSCLC after the failure of at least two systemic chemotherapies (progression after corresponding targeted therapy in patients who were positive for both EGFR mutation and ALK). The primary endpoint of this study was OS, and the secondary endpoints included PFS and ORR. Patients were randomized (2:1) into two groups: the treatment group received a daily dose of 12 mg of anlotinib for 2 consecutive weeks followed by 1-week discontinuation (n = 294); the control group received placebo (n = 143). The baseline characteristics (i.e., sex, age, stage, ECOG score, histological type, gene mutation status, and prior treatment history) were comparable between the two groups. The primary efficacy endpoint was analyzed in 292 surviving patients (66.82%) after a median duration of treatment of 6 cycles in the anlotinib group and 2 cycles in the placebo group. The anlotinib regimen showed a better median OS (9.46 months vs. 6.37 months), a 30% risk reduction in death (hazard ratio = 0.70), and a

1-year survival rate (39.53% vs. 27.79%), compared with the placebo. In addition, the data also showed that the efficacy of anlotinib was not affected by the mutational status of the EGFR driver gene, i.e., anlotinib could exert a good treatment effect regardless of the presence or absence of EGFR mutation.

At present, the treatment effect of second-line chemotherapy for patients with recurrence and metastasis is not satisfactory. Therefore, there is an urgent need to develop effective drugs to provide new treatment options for patients who have failed two or more lines of chemotherapy or targeted therapy. The efficacy and safety of anlotinib have been demonstrated in clinical studies of other tumors, and other anti-angiogenic target agents have also demonstrated antitumor activity against NPC. This study aims to further investigate the efficacy and safety of anlotinib in the treatment of patients with recurrent or metastatic NPC after failure of two or more lines of chemotherapy, so as to provide new treatment options for recurrent and metastatic NPC.

## **2. STUDY OBJECTIVES AND ENDPOINTS**

### **2.1 Primary Objective**

To evaluate the efficacy and safety of anlotinib hydrochloride in the treatment of patients with recurrent or metastatic nasopharyngeal carcinoma after failure second-line or above chemotherapy or targeted therapy.

### **2.2 Secondary Objectives**

- 1) To evaluate the long-term survival of patients.
- 2) To evaluate the quality of life of patients.

## **2.3 Study Endpoints**

### **2.3.1 Primary endpoints**

- DCR (perform efficacy evaluation according to RECIST v1.1; when the patient experiences objective remission for the first time, confirm after receiving two more courses of treatment)

### **2.3.2 Secondary endpoints**

- ORR, PFS, OS, CR, PR and DOR (according to RECIST v1.1)
- Safety and adverse events (according to NCI CTC AE v4.0)
- Quality of life assessment (FACT-H&N.V4 Quality of Life questionnaire)

## **3. STUDY POPULATION**

### **3.1 Target Population**

Patients with recurrent or metastatic nasopharyngeal carcinoma after failure of second-line or above chemotherapy or targeted therapy

### **3.2 Total Planned Enrollment**

A single-stage phase II design with a type I error of 5% and power of 80% was used to calculate the sample size. We considered the anlotinib treatment to be ineffective if DCR was  $\leq 20\%$  based on the result from the phase II study of gefitinib treatment for RM-NPC, and effective if DCR was  $\geq 40\%$  based on the DCR of 54.5% (95% CI, 38.0-70.2) achieved by pazopanib in RM-NPC patients. An estimated sample size of 35 patients was required. If at least 11 cases of CR or PR or SD were observed, the drug would be deemed effective. Assuming a dropout rate of 10%, the maximum

estimated sample size was 39 patients.

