### **9.3.3 Efficacy analysis**

In this single-arm study, the efficacy endpoints will be statistically analyzed using

descriptive statistics. PFS, OS, and DOR will be described using the Kaplan-Meier estimator, and median PFS, median OS, median DOR as well as ORR, DCR and 95% confidence interval will be calculated.

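### The success rule of at least 11 controlled patients does not hold the stated 5% type I error: it gives 7.5% at 35 patients, and 35 needs a cut-off of 12

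*Protocol*

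**What the plan says.** Protocol section 3.2 states the whole design in one paragraph. "A single-stage phase II design with a type I error of 5% and power of 80% was used to calculate the sample size". The treatment counts as ineffective at a DCR of 20% or less and as effective at 40% or more. "An estimated sample size of 35 patients was required". The decision rule follows: "If at least 11 cases of CR or PR or SD were observed, the drug would be deemed effective". A 10% dropout allowance then brings the maximum to 39. The paragraph does not name the test or say whether the 5% is one-sided or two-sided, and the rule gives a count without a denominator.

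Section 2.3.1 makes DCR the only primary endpoint. Section 9.2 analyses efficacy in the full analysis set, which is enrolled patients who received at least one dose, less significant violators of the entry criteria, and also in the per protocol set. Section 9.3.3 is descriptive: "median PFS, median OS, median DOR as well as ORR, DCR and 95% confidence interval will be calculated". It gives no other test or threshold for DCR.

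**The concern.** The error rate, the two DCR values, the sample size and the cut-off are all stated, so the cut-off can be checked directly. With 35 patients and a true DCR of 20%, 7 controlled patients are expected. A cut-off of 11 looks too close to 7 to be passed only 5% of the time. The missing denominator adds to this, because the same 11 becomes easier to reach as the number analysed rises towards 39.

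If the cut-off is too low, a drug at the protocol's own ineffective rate is declared effective more often than the protocol says. The trial has no comparator and no other stated criterion for DCR that would correct for this.

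**Working it through.** **Inputs, all from section 3.2:** p0 = 0.20, p1 = 0.40, type I error 5%, power 80%, n = 35, success if X ≥ 11, dropout 10%. The 5% is taken as one-sided, since the rule looks at the upper tail only.

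**Formula.** For X ~ Binomial(n, p), the error of a cut-off r is P(X ≥ r | n, 0.20) and its power is P(X ≥ r | n, 0.40).

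**Step 1: reproduce the sample size.** The search is for the smallest n that has some r with error ≤ 0.05 and power ≥ 0.80. It returns n = 35, and at that n the only qualifying cut-off is r = 12. Dropout: 35 / 0.90 = 38.9, rounded up to 39. Both printed sizes reproduce.

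**Step 2: evaluate the printed cut-off at n = 35.**

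| Rule | Error at DCR 20% | Power at DCR 40% |
|---|---|---|
| ≥ 11 of 35 | 7.47% | 88.8% |
| ≥ 12 of 35 | 3.44% | 80.5% |

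The printed rule has 7.47 / 5 = 1.5 times the stated error.

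**Step 3: vary the number analysed.**

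| n analysed | ≥ 11: error | ≥ 12: error / power | ≥ 13: error / power |
|---|---|---|---|
| 35 | 7.47% | 3.44% / 80.5% | 1.42% / 69.4% |
| 36 | 8.89% | 4.24% / 83.8% | 1.82% / 73.9% |
| 37 | 10.46% | 5.17% / 86.7% | 2.31% / 77.8% |
| 38 | 12.19% | 6.23% / 89.1% | 2.88% / 81.4% |
| 39 | 14.06% | 7.42% / 91.2% | 3.55% / 84.5% |

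A cut-off of 11 exceeds 5% at every n from 35 to 39. At 39 it is 14.06 / 5 = 2.8 times the stated error, and success would need an observed DCR of only 11/39 = 28%. Somewhat smaller sets do not rescue it: the error of 11 is 6.20% at n = 34 and 5.08% at n = 33.

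**Step 4: look for a method that gives both 35 and 11.**

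- An uncorrected one-sided normal approximation puts the boundary at n = 35 at 35 × 0.20 + 1.645 × √(35 × 0.20 × 0.80) = 7 + 1.645 × 2.37 = 10.9, so 11. The same approximation asks for only 29 patients.
- With continuity correction it asks for 34, and the arcsine version for 32.
- The two-sided normal approximation asks for 36. At n = 35 its boundary is 11.6, so 12.
- The exact design at one-sided 2.5% asks for 41 patients with a cut-off of 14.

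None of these gives 35 patients together with a cut-off of 11.

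**Step 5: compare with the interval estimate.** Section 9.3.3 names no interval method, so exact (Clopper-Pearson) intervals are assumed.

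| Result | Lower limit, two-sided 95% | Lower limit, two-sided 90% |
|---|---|---|
| 11/35 | 16.9% | 18.7% |
| 12/35 | 19.1% | 21.1% |
| 13/39 | 19.1% | 21.0% |

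The 90% interval is the one that corresponds to a one-sided 5% test. Its lower limit is below 20% at 11/35 and above 20% at 12/35 and 13/39.

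**The case against.** Five points can be made on the other side.

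- **The 14.1% is an upper bound.** The cut-off follows directly after the 35 patients and before the dropout allowance, so 11 of 35 is the natural reading. Undosed patients and significant violators of the entry criteria also leave the full analysis set. This stands: the firm figure is 7.5%, and 14.1% applies only if all 39 are counted. But dropouts who received a dose stay in that set, so a denominator above 35 is realistic and the rule should name it.
- **A 95% interval that includes 20% does not show that 11 is wrong.** This also stands. The exact 95% lower limit at 12/35 is 19.1%, so the corrected rule disagrees with that interval too. The case rests on the binomial error, which the 90% interval reflects.
- **Under an uncorrected one-sided normal test, 11/35 has a nominal p of 0.045.** That is so, but the true error of the resulting rule is still 7.47%, and that method does not lead to 35 patients. How the 11 arose cannot be known from the protocol.
- **The analysis is descriptive, and the verdict changes only at 11 of 35, or at 11 or 12 if 37 to 39 are analysed.** This limits the practical reach. It does not make the stated 5% correct, and the protocol does attach a declaration of efficacy to the count.
- **No cut-off at n = 37 meets both targets.** This is correct: 12 gives 5.17% error and 13 gives 77.8% power. It should be stated openly in the corrected rule.

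**Conclusion.** The concern holds. The sample size of 35 is right for the stated design, and the cut-off is one too low for it. As written, the only success rule for the only primary endpoint has an exact one-sided error of 7.5% against a stated 5%. The error rises to 14.1% if the bare count is applied to all 39 patients. The slip always acts in favour of declaring the drug effective.

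The result rests on the protocol's own 20% and 40%, on independent binomial outcomes and on a one-sided reading of the 5%. A two-sided reading leaves 2.5% for the upper tail and makes the gap wider.

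**What to change.** In section 3.2, replace the rule with at least 12 of 35 patients with CR, PR or SD, and state its exact properties: 3.4% one-sided error and 80.5% power. In addition:

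1. Name the analysis set that supplies the denominator, and print the cut-off for each possible number analysed: 12 for 35 or 36, and 13 for 37 to 39. State that at 37 the power is 77.8%, slightly below the target, because 12 would exceed 5%.
2. Say that the 5% is one-sided.
3. In section 9.3.3, report an exact two-sided 90% interval for DCR beside the 95% interval, so that one reported interval agrees with the decision rule.

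The cost is wording in the protocol and in any analysis plan, with no extra patients. Success needs one more controlled patient than now at 35 or 36 analysed, and two more at 37 to 39. Power at 35 falls from the 88.8% implied by the present rule to 80.5%, which is what the protocol says it planned.
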